Pulse rate	—	Pulse Rate
Basic waveform	—	—

Time from the start of the Q wave to the end of the T wave on the electrocardiogram	QT interval	QT Duration
QT interval corrected for heart rate	QTc	QTc Correction Method Unspecified

Study participation period

The duration of participation in this study for each subject is from the date of obtaining informed consent to the end of the prespecified final examination or withdrawal extirmination. The evaluation period is up to 24 weeks, and the period following the end of the evaluation period is defined as the extended administration period. The total duration of study drug administration is 52 weeks, consisting of the evaluation period and the extended administration period combined.

Timing of study drug administration, observation, and examination

Week 0 is defined as the day on which study drug administration is started (Day 1), and Week X is defined as the examination day X weeks after the start of study drug administration.

Baseline

Baseline values are defined as test values obtained before the start of study drug administration (Week 0).

Protocol Summary

I Study Title

An Intra-Subject Dose-Adjustment Study of KHK7580 for the Treatment of Hypercalcemia in Patients with Parathyroid Carcinoma or Primary Hyperparathyroidism Who Are Unable to Undergo Parathyroidectomy or Relapse After Parathyroidectomy

II Study Objectives

II-I Primary Objective

To evaluate the efficacy of KHK7580 orally administered for up to 24 weeks to patients with hypercalcemia in parathyroid carcinoma or PHPT who are unable to undergo PTx or relapse after PTx

II-II Secondary Objective

To evaluate the long-term safety and efficacy of KHK7580 orally administered to patients with hypercalcemia in parathyroid carcinoma or PHPT who are unable to undergo PTx or relapse after PTx

III Study Phase

Phase 3

IV Endpoints

IV-I Efficacy Evaluation

Primary endpoint

- Number and percentage of subjects whose corrected serum Ca level was maintained at ≤ 10.3 mg/dL for 2 weeks in the evaluation period

Secondary endpoints

- Number and percentage of subjects whose corrected serum Ca level was decreased by ≥ 1.0 mg/dL from baseline and remained decreased for 2 weeks in the evaluation period
- Corrected serum Ca level at each time point
- Intact PTH level at each time point
- Whole PTH level at each time point

IV-II Safety Evaluation

- Presence or absence of adverse events and adverse drug reactions, and the details thereof

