3.2 Endpoints

3.2.1 Efficacy Evaluation

3.2.1.1 Primary Endpoint

- Number and percentage of subjects whose corrected serum Ca level was maintained at ≤ 10.3 mg/dL for 2 weeks in the evaluation period

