to the extended administration period. If a subject did not enter the extended administration period, the reason will be recorded in the eCRF.

Subjects will visit the hospital once every 2 weeks during the evaluation period. In the extended administration period following the evaluation period, subjects should visit the hospital to undergo scheduled tests at Weeks 8, 12, 16, 20, 24, 28, 32, 36, 40, 44, 48, and 52. If the dose is increased or administration is resumed after an interruption, the date 2 weeks after the dose increase or resumption will be designated as the date of post-dose-increase (or post-resumption) visit, on which the subject should visit the hospital to undergo scheduled tests.

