9 OBSERVATION, INVESTIGATION, AND EXAMINATION ITEMS AND SCHEDULE

9.1 Schedule

Screening will be performed in subjects who have given their written informed consent. Afterwards, the study drug will be administered to subjects whose eligibility has been confirmed and for whom registration has been completed, and observation, investigation, and examination will be performed according to the schedule described in Table 9.1-1 and Table 9.1-2. Details are given in Section 9.3 “Observation and Investigation Items and the Timing Thereof” and Section 9.4 “Examination Items and the Timing Thereof.” Visits and examinations will be carried out on the scheduled visit dates with an allowable window of ± 4 days during the period between Week 2 and Week 24, and on the scheduled visit dates with an allowable window of ± 7 days thereafter. If a decision is made to discontinue study drug administration on a day of scheduled visit, the results of the examination on that scheduled visit date may be handled as the results of withdrawal examination.

Table 9.1-1. Observation, investigation, and examination schedule (evaluation period)

	Obtaining informed consent	Screening	Registration	Evaluation period														1 At discontinuation
				Time after administration of the study drug (Weeks)														
				0	2	4 ^e	6 ^e	8 ^f	10 ^f	12 ^g	14 ^g	16 ^h	18 ^h	20 ⁱ	22 ⁱ	24 ^j		
Time after administration (h)				Before administration	0.5	1	2	3										
Obtaining informed consent	X																	
Study drug administration					←												→	
Subject demographics	X ^a																	
Registration		X																
Height	X ^a																	
Body weight				X														X X
QOL assessment				X														X X
Vital sign				X				X X	X X	X X	X X	X X	X X	X X	X X	X X	X X	
Hematology				X				X X	X X	X X	X X	X X	X X	X X	X X	X X	X X	
Blood biochemistry 1	X ^b			X				X X	X X	X X	X X	X X	X X	X X	X X	X X	X X	
Blood biochemistry 2				X				X X	X X	X X	X X	X X	X X	X X	X X	X X	X X	
Urinalysis				X				X X	X X	X X	X X	X X	X X	X X	X X	X X	X X	
Plasma drug concentration ^c				X X X X	X X ^k			X ^k		X ^k		X ^k		X ^k		X ^k		
Pregnancy test ^d	X																	X
Electrocardiogram (12-lead)				X				X X	X X	X X	X X	X X	X X	X X	X X	X X	X X	
Adverse events					←												→	
Confirmation of the use status of concomitant medications	←																	→
Investigation of administration status					←												→	

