 l) If a decision is made to discontinue study drug administration on a day of scheduled visit, the results of the examination on that scheduled visit date may be handled as the results of withdrawal examination.

Table 9.1-2. Observation, investigation, and examination schedule (extended administration period)

	Extended administration period													^h At the first visit following dose increase or resumption after interruption	ⁱ At discontinuation		
	Time after the start of study drug administration (Weeks)																
	8 ^a	12 ^b	16 ^c	20 ^d	24 ^e	After the end of the evaluation period ^f				28 ^f	32	36	40	44	48	52	
Time after administration (h)						0.5	1	2	3								
Study drug administration (h)	←										→						X
Body weight					X												X
QOL assessment					X												X
Vital sign	X	X	X	X	X					X	X	X	X	X	X	X	X
Hematology	X	X	X	X	X					X	X	X	X	X	X	X	X
Blood biochemistry 1	X	X	X	X	X					X	X	X	X	X	X	X	X
Blood biochemistry 2	X	X	X	X	X					X	X	X	X	X	X	X	X
Urinalysis	X	X	X	X	X					X	X	X	X	X	X	X	X
Plasma drug concentration ^g	X ⁱ	X ⁱ	X ⁱ	X ⁱ	X ⁱ	X	X	X	X								
Pregnancy test ^k																	X
Electrocardiogram (12-lead)	X	X	X	X	X					X	X	X	X	X	X	X	X
Adverse events	←																→
Confirmation of the use status of concomitant medications	←																→
Investigation of administration status	←																→

The allowable window for the scheduled visit dates is ± 4 days until Week 24 and ± 7 days thereafter.

a) For subjects who completed the evaluation period in Week 4 or 6, hospital visits in the extended administration period will start in Week 8.
 b) For subjects who completed the evaluation period in Week 8 or 10, hospital visits in the extended administration period will start in Week 12.
 c) For subjects who completed the evaluation period in Week 12 or 14, hospital visits in the extended administration period will start in Week 16.
 d) For subjects who completed the evaluation period in Week 16 or 18, hospital visits in the extended administration period will start in Week 20.

- e) For subjects who completed the evaluation period in Week 20 or 22, hospital visits in the extended administration period will start in Week 24.
- f) For subjects who completed the evaluation period in Week 24, hospital visits in the extended administration period will start in Week 28.

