13.1.1 Efficacy Evaluation

13.1.1.1 Primary Evaluation

- The number and percentage of subjects whose corrected serum Ca level was maintained at ≤ 10.3 mg/dL for 2 weeks in the evaluation period will be calculated, along with the exact 95% confidence interval. Whether or not the lower limit of the exact 95% confidence interval exceeds the threshold ratio of 11% will be used as a criterion for judging the efficacy.

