13.5 Procedures for Handling Missing, Rejected, and Abnormal Data

For the analyses specified in Section 13.1, failure to obtain evaluable data for two consecutive weeks regarding the binary response variables for the percentage of subjects in the primary and secondary endpoints will be handled as an “unachieved” subject. Any missing value in continuous data will be handled as missing data, and no special complementary processing by a statistical method will be performed. If any specific handling of the data becomes necessary due to unforeseen events that were not expected at the start of the study, the handling method will be determined before database lock and described in the analysis plan.

13.6 Procedures for Preparing the Analysis Plan and Reporting Deviations from the Original Plan

The details of the final analysis plan, including the analyses shown in Section 13.1, will be finalized as the analysis plan by the time of database lock. Major changes to the analysis plan will be described in the clinical study report.

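### Do the ±4-day visit windows leave the two-week calcium response undefined?

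*Combined protocol and SAP*

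**What the plan says.** Section 3.2.1.1 defines response as corrected calcium "maintained at ≤ 10.3 mg/dL for 2 weeks in the evaluation period". The secondary responder endpoint in Section 3.2.1.2 (a fall of at least 1.0 mg/dL) uses the same two-week condition, and so does the rule in Section 4.1 that moves a responder to the extended administration period.

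On timing, the definitions ahead of the Protocol Summary state that "Week X is defined as the examination day X weeks after the start of study drug administration". Section 4.1 adds: "Subjects will visit the hospital once every 2 weeks during the evaluation period". Section 9.1 allows each visit to move, "with an allowable window of ± 4 days during the period between Week 2 and Week 24"; Week 0 has no window.

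In Table 9.1-1, footnotes e to j attach the transfer rule to the visit columns from Week 4 to Week 24 and name a fixed next visit for each. Table 9.1-2 lists completion of the evaluation period only at visit weeks, beginning with "For subjects who completed the evaluation period in Week 4 or 6".

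Section 13.5 classes a subject as not having achieved the endpoint on "failure to obtain evaluable data for two consecutive weeks regarding the binary response variables". Section 13.6 says the analytical details "will be finalized as the analysis plan by the time of database lock". Efficacy is judged in Section 13.1.1.1 by "Whether or not the lower limit of the exact 95% confidence interval exceeds the threshold ratio of 11" per cent. Sections 13.2 and VIII set the target at 10 or more treated subjects.

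The contents list a rationale for the efficacy endpoints (Section 24.8), but the text of Section 24 is not in the public copy, and neither is the separate analysis plan.

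**The concern.** The endpoint gives a duration, while the data are point measurements whose spacing can vary widely. It states neither a number of visits nor a minimum number of days. Two low values 8 days apart are a response if visits are counted and may not be if days are counted.

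Three features make this look more than cosmetic:

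- The missing-data rule speaks of weeks, not visits, which seems to lean toward elapsed time.
- A responder transfers at once, so a short first pair gets no further evaluation-period value to lengthen it. The next calcium value belongs to the extended period, outside the endpoint.
- Details need only be settled by database lock. In an uncontrolled study, calcium values and sample dates are in the eCRF before then.

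At the target size, one reclassified subject can change the primary conclusion, and a switch of reading would affect every responder with a short pair together.

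**Working it through.** **1. Spacing of visits.** Inputs: nominal spacing 14 days (Section 4.1) and offsets *a* (earlier visit) and *b* (later visit), each from −4 to +4 days (Section 9.1).

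Gap = 14 + (*b* − *a*). Minimum 14 − 8 = 6 days; maximum 14 + 8 = 22 days. For Week 0 to Week 2, with no window at Week 0, the range is 10 to 18 days.

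**2. How often a pair is under 14 days.** The documents give no visit-timing data, so these are assumptions:

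- All visits on time, or all shifted alike: 0%.
- Rounded normal offsets limited to ±4, independent: 24.2% (SD 0.5 day), 36.5% (SD 1), 42.7% (SD 2). Correlation between consecutive offsets lowers these; at 0.8 they are 12.4%, 23.6% and 34.6%.
- Uniform and independent: 36 of the 9 × 9 = 81 offset pairs, 44.4%.

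**3. The success criterion.** Exact (Clopper-Pearson) 95% lower limits against 11%:

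| Responders / N | Lower limit | Criterion |
|---|---|---|
| 3/10 | 6.7% | not met |
| 4/10 | 12.2% | met |
| 4/11 | 10.9% | not met |
| 5/11 | 16.7% | met |

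**4. What the readings could do to the verdict.** Let *p* be the true response rate by visits and *q* the share of responders whose pair is under 14 days and who are lost under a strict day count. With X ~ Bin(10, *p*) and Y ~ Bin(10, *p*(1 − *q*)), the chance of different verdicts is P(X ≥ 4) − P(Y ≥ 4).

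| *q* | *p* = 0.4 | 0.5 | 0.6 | 0.7 |
|---|---|---|---|---|
| 0 | 0% | 0% | 0% | 0% |
| 0.10 | 10% | 9% | 6% | 2% |
| 0.242 | 26% | 26% | 20% | 12% |
| 0.365 | 38% | 43% | 38% | 27% |
| 0.444 | 45% | 54% | 50% | 40% |

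This assumes that sites transfer on two visits, that the analysis then applies a strict 14-day rule, and that short pairs are unrelated to response. It also counts a 13-day pair as failure. With one day of tolerance (short means 12 days or fewer, independent offsets), the share falls from 24.2% to 2.7% at SD 0.5 and from 36.5% to 14.9% at SD 1. At *q* = 0.027 the chances become 2.7, 2.3, 1.3 and 0.5%; at *q* = 0.149 they are 16, 15, 10 and 5%.

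**5. Which reading the documents support.**

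- Week X is an examination day, and a visit inside its window counts as that week's visit. Two consecutive visit weeks are then two weeks apart in the plan's own units.
- Transfer is tied to visit columns, and its first possible point is Week 4, which matches the Week 2 and Week 4 pair.
- No footnote says what to do with a pair inside both windows but under 14 days apart.
- Section 13.5 concerns failure to obtain data. A subject with evaluable calcium at two consecutive in-window visits has not failed to provide data. Read as two adjacent calendar weeks, the phrase could not be met by on-time visits, which are 14 days apart. Consecutive visit weeks is the reading that fits the schedule.

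**6. Direction of the choice.** If no visits are missed, values that stay at or below 10.3 mg/dL over 14 or more days include at least one consecutive pair of low visits. Every responder by days is then also a responder by visits, and the visit count is equal or higher.

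**The case for a change.** The strongest case for acting is that the endpoint sections are silent, the missing-data rule can be parsed against the schedule, and the criterion turns on a single subject. One sentence would settle it, and sensitivity counts would need only sample dates and values already collected.

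The silence is real, and so is the sensitivity of the criterion: 4/10 passes and 3/10 fails. The tolerance argument is also only partial, since with visit-day SD 1 about 15% of pairs would still be 12 days or fewer. Section 13.5 is ambiguous as worded.

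The step from ambiguity to a threatened result does not stand. It needs an analyst to pass over the visit-based schedule and impose a strict 14-day cutoff that no readable section states. The worry about a late choice points the wrong way as well: the reading that favours success is the one the schedule already implies, and it is also the definition one would write down in advance. Writing it down would leave the primary count as it is. A count restricted to pairs of 14 or more days is a reasonable optional extra. A count that draws on extended-period values would go outside the endpoint as defined.

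**Conclusion.** No change to the plan is needed. The 6-to-22-day range is correct, and the readable text does not spell out the two-week condition. The schedule nevertheless gives one workable reading: the criterion is met at two consecutive scheduled evaluation-period visits, each within its window. Sites and analysts following the schedule would apply it to both responder endpoints and to transfer, and the primary count would match the one from an explicit definition.

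The percentages in the working describe a disagreement with a rule the documents do not contain, so they do not measure a risk in this plan. The conclusion rests on the schedule governing the reading of Section 13.5 and, for the direction of any late choice, on no missed visits within the qualifying span. It would change only if the separate analysis plan or the Section 24 rationale, neither of which is readable here, set a minimum number of elapsed days while transfer stayed tied to visits.

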9.2 Subject Demographics

The following items will be investigated and entered into the eCRF.

- Date of informed consent
- Sex
- Date of birth
- Medical history – Complication
- Medical history – Past medical history
- Medical history – Primary disease
- Date of diagnosis for primary disease
- Occurrence of pharmacotherapy for primary disease/PTx/parathyroid intervention therapy and start date of procedure
- Use status of cinacalcet hydrochloride (cinacalcet hydrochloride before screening)
 - Total daily dose
 - Dosage (dosing frequency per interval)
 - Dosing period (start date of medication and end date of medication)
 - Reason of medication stopped
 - UGI tract disturbance due to cinacalcet hydrochloride
- Other items related to the inclusion and exclusion criteria

Visit [allowable window]: At the time of screening [from the time of obtaining consent until before the start of study drug administration (Week 0)]

9.3 Observation and Investigation Items and the Timing Thereof

9.3.1 Exposure

The following items will be entered into the eCRF for each scheduled visit date.

- Start date of treatment
- End date of treatment
- Dosage and administration*¹ (planned dosing frequency and dose)
- Status of study drug administration (number of tablets taken [actual dose] and compliance*²)
- Date and time when the study drug was taken*³

*¹: If the dose was reduced or study drug administration was interrupted, the reason will be investigated and entered into the eCRF. For dose reduction or interruption due to an adverse event, the details of the adverse event will be entered into the eCRF.

*²: Only for 1 week prior to plasma drug concentration measurement. The date on which the subject took the study drug in accordance with the dosage and administration specified by his/her doctor will be designated as the study drug compliance date, and the status of study drug compliance for 1 week prior to plasma drug concentration measurement will be recorded in the eCRF on a daily basis.

*³: Only on the scheduled visit dates on which the plasma drug concentration is measured. The date and time of study drug administration immediately before plasma drug concentration measurement (latest date/time of administration before specimen collection), and, for Week 0 and the date of

plasma drug concentration measurement after the end of the evaluation period, the time of study drug administration on that day (latest time of administration before specimen collection of 0.5h/1h/2h/3h on the specimen collection day) will be entered into the eCRF.

Visit: [Evaluation period] Weeks 0, 2, 4, 6, 8, 10, 12, 14, 16, 18, 20, 22, and 24, and at the time of discontinuation

[Extended administration period] Weeks 8, 12, 16, 20, 24, 28, 32, 36, 40, 44, 48, and 52, at the first visit following dose increase or resumption after interruption, and at the time of discontinuation

Allowable window: Within 4 days before and after the scheduled visit dates during the period from Week 2 to Week 24, and within 7 days before and after the scheduled visit dates thereafter

9.3.2 QOL Assessment (EQ-5D-5L)

A five-item questionnaire survey on health condition will be conducted, and the results will be entered into the eCRF. In the questionnaire, the answer best representing the health condition on the day of the survey will be selected from among five options.

The health condition on the day of the survey will also be assessed using a visual analogue scale, and the results will be entered into the eCRF.

Visit: Weeks 0, 24, and 52, and at the time of discontinuation

Allowable window: Within 4 days before and after the scheduled visit date in Week 24, and within 7 days before and after the scheduled visit date in Week 52

9.4 Examination Items and the Timing Thereof

9.4.1 Laboratory Tests

In order to determine whether there are any changes in laboratory values after study drug administration, tests will be performed according to the prespecified testing schedule, and the date of testing (date of sample collection) and test results (except for screening tests) will be entered into the eCRF. The tests in Week 0 will be performed before the first administration of the study drug. All laboratory tests, except for intact PTH and whole PTH levels, will be performed at the study site. Intact PTH and whole PTH levels will be measured at a central laboratory, and the results will be reported to the study site and sponsor. The allowable window for the timing of measurement of test items will be within 4 days before and after the scheduled visit dates during the period from Week 2 to Week 24, and within 7 days before and after the scheduled visit dates thereafter.

9.4.1.1 Hematology

Test items: WBC, WBC fraction (Baso, Eosino, Neutro, Mono, and Lymph), RBC, Ht level, Hb concentration, and PLT

Visit: [Evaluation period] Weeks 0, 2, 4, 6, 8, 10, 12, 14, 16, 18, 20, 22, and 24, and at the time of discontinuation

[Extended administration period] Weeks 8, 12, 16, 20, 24, 28, 32, 36, 40, 44, 48, and 52, at the first visit following dose increase or resumption after interruption, and at the time of discontinuation

9.4.1.2 Blood Biochemistry 1

Test items (in-hospital measurement): T-Cho, TG, TP, BUN, UA, Cr, T-Bil, AST, ALT, γ -GTP, LDH, ALP, CK, Na, K, Cl, Mg, corrected serum Ca^{*1}, Ca, Alb, and P

Visit: At the time of screening^{*2}

[Evaluation period] Weeks 0, 2, 4, 6, 8, 10, 12, 14, 16, 18, 20, 22, and 24, and at the time of discontinuation

[Extended administration period] Weeks 8, 12, 16, 20, 24, 28, 32, 36, 40, 44, 48, and 52, at the first visit following dose increase or resumption after interruption, and at the time of discontinuation

*1: If the serum Alb value is less than 4.0 g/dL, the serum Ca level will be corrected according to the following formula. If the serum Alb level is 4.0 g/dL or higher, the actual serum Ca level will be handled as the corrected serum Ca level.

Corrected serum Ca level (mg/dL) = actual serum Ca level (mg/dL) + 4 - serum Alb value (g/dL)

*2: Ca, corrected serum Ca level, and Alb will be measured. In the event that the test result does not meet inclusion criteria 4), re-testing may be performed. If performed in Week 0, it will be handled as a test result in Week 0.

9.4.1.3 Blood Biochemistry 2

Test items (central measurement): Intact PTH and whole PTH levels

Visit: [Evaluation period] Weeks 0, 2, 4, 6, 8, 10, 12, 14, 16, 18, 20, 22, and 24, and at the time of discontinuation

[Extended administration period] Weeks 8, 12, 16, 20, 24, 28, 32, 36, 40, 44, 48, and 52, at the first visit following dose increase or resumption after interruption, and at the time of discontinuation

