3.2.1.2 Secondary Endpoints

- Number and percentage of subjects whose corrected serum Ca level was decreased by ≥ 1.0 mg/dL from baseline and remained decreased for 2 weeks in the evaluation period
- Corrected serum Ca level at each time point
- Intact PTH level at each time point
- Whole PTH level at each time point

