6.2 Inclusion Criteria

Subjects enrolled in this study should satisfy all of the following criteria.

- 1) Personally submitted written voluntary informed consent to participate in the study
- 2) Aged \geq 20 years at the time of consent
- 3) A diagnosis of parathyroid carcinoma or PHPT who are unable to undergo PTx or relapse after PTx
- 4) Corrected serum Ca level > 11.3 mg/dL at screening

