The allowable window period is ± 4 days of the scheduled visit dates (except for Week 0).

a) Performed after informed consent is obtained and before the start of study drug administration (Week 0).

b) Corrected serum Ca, Ca, and Alb levels will be measured. In the event that the test result does not meet inclusion criteria 4), re-testing may be performed. If performed in Week 0, it will be handled as a test result in Week 0.

c) From Week 2 onwards, if a subject is not taking the study drug as of the day before his/her visit to the hospital, it is permissible not to perform blood collection on the day of hospital visit. It is also permissible not to perform post-dose blood collection in a subject for whom a decision to interrupt study drug administration has been made on the day of hospital visit.

d) Female subjects only. However, no pregnancy test is required if at least 12 months have passed since the last menstrual period without any other medical reason.

e) Subjects whose corrected serum Ca level has been maintained at ≤ 10.3 mg/dL for 2 weeks will immediately transition to the extended administration period, with the next visit being Week 8.

f) Subjects whose corrected serum Ca level has been maintained at ≤ 10.3 mg/dL for 2 weeks will immediately transition to the extended administration period, with the next visit being Week 12.

g) Subjects whose corrected serum Ca level has been maintained at ≤ 10.3 mg/dL for 2 weeks will immediately transition to the extended administration period, with the next visit being Week 16.

h) Subjects whose corrected serum Ca level has been maintained at ≤ 10.3 mg/dL for 2 weeks will immediately transition to the extended administration period, with the next visit being Week 20.

i) Subjects whose corrected serum Ca level has been maintained at ≤ 10.3 mg/dL for 2 weeks will immediately transition to the extended administration period, with the next visit being Week 24.
 j) Subjects whose corrected serum Ca level has been maintained at ≤ 10.3 mg/dL for 2 weeks will immediately transition to the extended administration period, with the next visit being Week 28.
 k) If the subject transitions to the extended administration period, plasma drug concentrations may be measured at the end of the evaluation period (0.5, 1, 2, and 3 hours) (see Table 9.1-2 "Observation, investigation, and examination schedule (extended administration period)").

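### Where the calcium sample that qualified a subject (> 11.3 mg/dL) is drawn in Week 0, it is also the baseline, so corrected Ca change and the ≥ 1.0 mg/dL responder endpoint are biased upward for those subjects

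*Combined protocol and SAP*

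**What the plan says.** - Inclusion criterion 4 (6.2) requires "Corrected serum Ca level > 11.3 mg/dL at screening".
- 9.4.1.2 note *2, repeated in Table 9.1-1 footnote b, covers the screening calcium and albumin: "In the event that the test result does not meet inclusion criteria 4), re-testing may be performed". No limit on the number of re-tests is given. The next sentence reads "If performed in Week 0, it will be handled as a test result in Week 0".
- The definitions at the front of the protocol make Week 0 the first dosing day (Day 1) and make the pre-dose Week 0 value the baseline. Nothing requires that value to come from a different sample than the one used for eligibility.
- Baseline enters the first secondary endpoint, the number and percentage of subjects whose corrected Ca "decreased by ≥ 1.0 mg/dL from baseline and remained decreased for 2 weeks" (3.2.1.2, 13.1.1.2), and the corrected Ca change summaries (13.1.1.2).
- 9.4.1 says that dates and "test results (except for screening tests) will be entered into the eCRF".
- When screening is on an earlier day, Table 9.1-1 schedules a separate pre-dose Week 0 biochemistry sample, which does not have to exceed any limit.

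**The concern.** A measurement accepted only because it lies above a cut-off is, on average, above the subject's own usual level. If the same measurement is the baseline, the next measurements fall back toward that level and the fall is counted as response. A randomised control group would show the same fall and cancel it. This study has one arm, so the error stays in the result, and it favours the drug.

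Two features add to this. The target is at least 10 treated subjects (13.2), so one reclassified subject in 10 moves a rate by 10 percentage points. And for an affected subject the two responder endpoints are no longer distinct: baseline is above 11.3 and the primary endpoint needs values of 10.3 or less, so the fall exceeds 11.3 − 10.3 = 1.0 mg/dL and every primary responder is automatically a ≥ 1.0 mg/dL responder. With a separate baseline this is not automatic.

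**Working it through.** **Inputs.** From the protocol: cut-off 11.3 mg/dL, response threshold 1.0 mg/dL held for 2 weeks, visits every 2 weeks to Week 24 (12 post-dose visits). Not in the protocol, therefore assumed: within-subject SD σ of 0.2 to 0.5 mg/dL, the distribution of true calcium, the drug effect, and the share of subjects with a shared sample. The protocol gives no figure for this bias, so there is none to reproduce.

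**Step 1: inflation per affected subject.** For true level T and independent normal errors, a qualifying value exceeds T on average by σ·φ(z)/[1 − Φ(z)], with z = (11.3 − T)/σ.

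- T = 11.5, σ = 0.2: z = −1.00; 0.2 × 0.2420/0.8413 = 0.06 mg/dL
- T = 11.5, σ = 0.3: z = −0.667; 0.3 × 0.3194/0.7475 = 0.128 mg/dL
- T = 11.5, σ = 0.5: z = −0.40; 0.5 × 0.3683/0.6554 = 0.28 mg/dL
- T = 12.0, σ = 0.3: z = −2.333; 0.3 × 0.0262/0.9902 = 0.01 mg/dL
- T = 12.0, σ = 0.5: z = −1.40; 0.5 × 0.1497/0.9192 = 0.08 mg/dL
- T = 11.2, σ = 0.3 and 0.5: 0.31 and 0.46 mg/dL

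For a fixed T the number of tests does not enter: whichever test passes is a draw conditional on exceeding 11.3. Re-testing raises the average only by admitting more subjects near the cut-off (0.10 to 0.13 mg/dL at σ = 0.3 in the model of step 2).

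**Step 2: responder rate.** Simulation with true level 11.1 + exponential (mean 0.6), up to three tests, a constant fall over 12 visits, and response defined as two consecutive values at least 1.0 below baseline. Every subject is taken as affected.

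| σ | True fall (mg/dL) | Qualifying sample as baseline | Separate Week 0 sample |
|---|---|---|---|
| 0.4 | 0 | 7.4% | 4.8% |
| 0.3 | 0.5 | 27% | 18% |
| 0.4 | 0.5 | 43% | 29% |
| 0.3 | 0.8 | 66% | 49% |
| 0.3 | 1.0 | 85% | 71% |
| 0.3 | 1.5 | 99.5% | 98% |
| 0.4 | 1.5 | 98.9% | 95.5% |

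A second model with normally distributed true levels (means 11.0 to 12.0, σ 0.2 to 0.5, none or two re-tests) gives a bias of 0.02 to 0.45 mg/dL per affected subject. For a true fall of 0.8 the rates run from 39.8% against 37.0% to 89.1% against 58.0%. With a separate sample the simulated bias is zero within 0.005 mg/dL.

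**Step 3: dilution.** The gap in the whole study is the gap above times the share affected. At an assumed 20%, the 9 points at a fall of 0.5 (27% − 18%) become about 2 points, or 0.2 of a subject in 10.

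**Step 4: what the remedies can do** (T = 11.5, σ = 0.3).

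- A second tube on the same day shares that day's fluctuation. At an assumed correlation of 0.7, 0.7 × 0.128 = 0.09 mg/dL of the bias remains.
- Averaging all pre-dose values, failed tests included, also helps only in part. A pass averages +0.128 and a fail −0.3 × 0.3194/0.2525 = −0.379. With up to three tests, the average deviation is +0.128 after a first-test pass (probability 0.7475), (0.128 − 0.379)/2 = −0.126 after one fail (0.1887), and (0.128 − 0.758)/3 = −0.210 after two (0.0477). The weighted mean is (0.0957 − 0.0238 − 0.0100)/0.9839 = 0.06 mg/dL, about half the bias.

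**The case against.** **Reach.** A reader might infer that every change from baseline is inflated. The documents do not support that. Subjects screened on an earlier day have the separate Week 0 sample, and intact and whole PTH are neither in the screening panel nor eligibility variables. A reader might also infer that the study's success criterion is compromised. It is not: the primary endpoint uses an absolute 10.3 mg/dL limit, and the 11% threshold (13.1.1.1) is applied to that rate. The affected results are descriptive secondary summaries with no success criterion. All of this stands and sets the scope.

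**Frequency.** Registration must follow known screening results and goes by fax to a centre that may raise queries before the dosing date (8.2). Same-day screening and dosing is permitted, and calcium is measured at the site, but it need not be common. This stands; the share is unknown.

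**Effect size.** The dose is titrated upward while calcium exceeds 10.3 (7.1.1.2.1), so many subjects may fall by well over 1.0 mg/dL, where the responder gap nearly vanishes. This stands for the responder endpoint at falls of 1.5 or more. It does not hold at 1.0 (85% against 71%), and it does not remove the bias in mean corrected Ca change, which does not depend on the drug effect.

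**Visibility.** It would be too strong to say that the analyst cannot see the problem. A sample handled as the Week 0 result is entered with its collection date, and 9.2 asks for other items related to the entry criteria. But failed earlier values need not be entered, and no marker for a shared sample is described.

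**Conclusion.** The rule permits a selected value to serve as baseline, and for subjects to whom it applies the bias in corrected Ca change and in the ≥ 1.0 mg/dL responder endpoint runs in the drug's favour. The direction is certain; the size is not. It is small for true levels well above 11.3 or a within-subject SD near 0.2 mg/dL. It is material for subjects near the cut-off with modest falls.

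The figures rest on assumed SDs, assumed calcium distributions, independent errors and a constant fall. They ignore titration and early transfer to the extended administration period. The percentages also assume that every subject is affected and must be scaled by the true share. This is a cheap improvement to secondary results, not a threat to the primary conclusion.

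**What to change.** 1. In 9.4.1, lift the exclusion of screening tests for calcium and albumin: enter every screening and re-test value, with its date, in the eCRF.
2. Flag each subject whose qualifying sample is also the baseline.
3. Report the ≥ 1.0 mg/dL endpoint and the corrected Ca changes also (a) without flagged subjects and (b) with the baseline of flagged subjects taken as the mean of all their pre-dose values, failed tests included. Analysis (a) removes the shared baselines but leaves fewer than the already small number of subjects. Analysis (b) keeps everyone but removes only part of the bias, and changes nothing for a subject whose only pre-dose sample passed.
4. State that, where screening is on an earlier day, the scheduled separate Week 0 pre-dose sample is the baseline and is not averaged with the screening value.
5. Optionally, draw a second pre-dose tube for subjects tested on Day 1 (Table 9.6-1 lists 2 mL for the screening tube). As step 4 of the working shows, this removes only part of the bias.

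The cost is a few eCRF fields and one sensitivity table, with no extra blood unless item 5 is adopted. The secondary result may look slightly less favourable.
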